- 1. Evaluate impact of OAB on quality of life using the incontinence impact questionnaire
- 2. Compare the number of voids per 24-hour periods
- 3. Compare the number of nighttime voids
- 4. Compare the number of incontinence episodes

Study Design and Methods:

This will be a randomized study of patients with overactive bladder not naive to behavioral therapy and/or pharmacotherapy (or unable to tolerate or with contraindications to pharmacotherapy) with or without urge incontinence recruited through the outpatient offices of the Division of Urogynecology at Women and Infants Hospital and University of Pittsburgh Medical Center Magee-Womens Hospital. The patients will be randomized to receiving unilateral or bilateral PTNS for 30 minutes weekly for a total of 12 weeks. Though we considered the use of a sham needle to decrease participants' bias in reporting their results, we have elected not to use a sham needle. Since all participants will be naïve to PTNS, they are unable to gauge the amount of improvement they should have and therefore we can expect reported improvement to be accurate.

Participants will be asked to complete a 2-day bladder diary at baseline and weekly as per routine PTNS care. Participants will also be asked to fill out a validated OAB symptom severity questionnaire (OAB-q) and the incontinence impact questionnaire (IIQ-7) at baseline (+/- 1 week), four weeks (+/- 1 week), eight weeks (+/- 1 week) and twelve weeks (+/- 1 week).

Our primary outcome will be the improvement in symptom severity as measured by the OAB-q score.

Secondary outcomes will include change in the number of daily voids, change in nocturia or night time voids, change in number of incontinence episodes as measured by the bladder diary and, impact in quality of life as demonstrated by change in score of the incontinence impact questionnaire, IIQ-7.

All questionnaires collected from participants will be labeled with a unique study number and any participant identifiers on the questionnaires or voiding diary will be redacted prior to saving in a research folder in a locked drawer.

Inclusion criteria

Female patients over the age of 18 who have previously tried and failed, or were unable to tolerate, behavioral therapy. Patients will have to consent to participate in the study. Patients on pharmacologic therapy at the time of recruitment will continue their treatment.

Exclusion criteria

- 1. Pregnant patients

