- 2. Patients with pacemakers of implantable defibrillators
- 3. Patients with neurogenic bladder
- 4. Patients who have received Botox or have an implant for sacral nerve stimulation
- 5. Patients with uncontrolled bleeding disorder
- 6. Patients with unhealed ulcers or with leg edema surrounding medial malleolus

Rationale for exclusion criteria

PTNS is an approved procedure that was not previously studied in the pregnant population therefore we will exclude pregnant patients from this study. PTNS is the electrical stimulation of the tibial nerve through a needle and therefore it is unclear how this stimulation would interact with a pacemaker or implantable defibrillator.

While patients with neurogenic bladder may have overactive bladder, the pathophysiology of their urinary frequency and incontinence is different therefore including them in this particular study has the potential to confuse the study results. Botox and Interstim (implantable sacral nerve stimulator) are advanced overactive bladder therapies and are generally offered to those who have failed pharmacotherapy and PTNS and therefore PTNS is unlikely to be effective in participants that have failed more advanced therapies. A needle is inserted through the skin for PTNS and thus PTNS conjures a potential for bleeding. Therefore, those with bleeding disorders will be excluded. Electrical stimulation is sent to the tibial nerve through a needle and therefore leg ulcers and edema can potentially alter the stimulation received by the nerve.

Sample Size calculations

Based on the SUmiT trial results, we expect a decrease in OAB symptom severity of 36.7 with a standard deviation of 21.5 in the unilateral PTNS group. If we estimate that the bilateral PTNS group will show at least 50 % improvement from the unilateral, then we should see an average decrease in in symptom severity of 55 in the bilateral PTNS group.

Our sample size estimate based on 5% significance and 80 % power with a standard deviation of 21.5 will be: 23 per group for a total of 46 participants.

If we expect an attrition rate of about 10%, our goal is therefore to recruit a total of 50 participants with 25 participants in each arm.

Statistical Analysis

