Descriptive statistics will be used to assess the balance of baseline characteristics between randomization groups: unilateral and bilateral PTNS groups. The primary analysis will be intent-to-treat. At baseline, for both treatment groups, the Wilcoxon-rank sum test will be used for all continuous variables and Fisher's exact test for all categorical variables. For the analysis of primary and secondary outcomes, we will compare the last measurement to the baseline measurement within and between treatment groups in OABq score, IIQ-7, daily number of voids, number of nighttime voids, and number of incontinence episodes between the unilateral and bilateral PTNS groups using a pairwise t-test (using a Bonferroni adjustment). These comparisons will result in three sub-analyses: the changes of the primary and secondary outcomes within the unilateral PTNS group, within the bilateral PTNS group, and between the groups (taking the differences between the baseline and last measurement between the groups).

Recruitment and enrollment

Patients with overactive bladder or urge urinary incontinence who have failed behavioral or pharmacologic therapy will have all advanced therapy options presented to them as part of their clinical care by their physician. Those who choose to have PTNS will be approached about the study either by the physician or the research coordinator. If the patient meets eligibility and wishes to participate, they will be consented. In addition, patients who present for their first PTNS visit but were not previously approached about this study will be asked about participating in the study and consented if they are willing

Randomization

Randomization has been performed by a member of the staff at Women and Infants Hospital not part of the research team. Randomization has been concealed in opaque envelopes. Assignment of the randomization envelope to each subject will occur after the patient has signed consent.

Intervention

There will be 12 weekly PTNS treatments of 30 minutes. At the first visit, the participant will complete the OAB questionnaire and the incontinence impact questionnaire. This will be repeated at weeks 4, 8 and 12.

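### The trial is sized at an unadjusted 5% level, but the analysis puts the primary OAB-q test under a Bonferroni adjustment of unstated size, so the stated 80% power does not hold as written

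*Combined protocol and SAP*

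**What the plan says.** Study Design and Methods names one primary outcome: "Our primary outcome will be the improvement in symptom severity as measured by the OAB-q score". Sample Size calculations sizes the trial on that outcome alone: "Our sample size estimate based on 5% significance and 80 % power with a standard deviation of 21.5 will be: 23 per group". To allow for about 10% attrition, "our goal is therefore to recruit a total of 50 participants with 25 participants in each arm". That section mentions neither multiplicity nor whether the test is one- or two-sided.

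Statistical Analysis gives one rule for all outcomes together. It opens "For the analysis of primary and secondary outcomes, we will compare the last measurement to the baseline measurement", lists five outcomes with the OAB-q first (then IIQ-7, daily voids, nighttime voids and incontinence episodes), and compares them within and between groups, ending "between the unilateral and bilateral PTNS groups using a pairwise t-test (using a Bonferroni adjustment". The next sentence says "These comparisons will result in three sub-analyses: the changes of the primary and secondary outcomes within the unilateral PTNS group", followed by the same within the bilateral group and between the groups, the last defined as "taking the differences between the baseline and last measurement between the groups". The document nowhere gives the number of tests, the adjusted alpha, or an exemption for the between-arm OAB-q comparison.

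**The concern.** The sample size calculation spends the full 5% on one test. The analysis rule, read as it stands, divides that 5% among several tests, one of which is the primary. If the rule is followed, the trial has less power than it claims. If it is not, the primary is tested at a level that the analysis section does not give.

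The same data could therefore yield opposite answers to the trial's main question. A between-arm OAB-q p-value of 0.02 is positive at 0.05 and negative at 0.0167, 0.01 or 0.0033. If the choice among these is left until the p-value is known, the result can determine the threshold.

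**Working it through.** **Inputs.** From Sample Size calculations: mean decrease 36.7 (unilateral) and 55 (bilateral), SD 21.5 taken as common to both arms, 23 per group analysed, 25 per group recruited. From Statistical Analysis: five outcomes and three sub-analyses. Assumption: two-sided testing, which the plan does not state.

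**Method.** Two-sample t-test on change from baseline. The difference is δ = 55 − 36.7 = 18.3, so d = 18.3/21.5 = 0.851. With n per arm, degrees of freedom are 2n − 2 and the noncentrality is δ / (SD × √(2/n)). Power is the probability that a noncentral t with these parameters exceeds the two-sided critical value at α = 0.05/m, where m is the number of tests in the Bonferroni family.

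**Step 1: reproduce the plan's figure.** At n = 23 the noncentrality is 18.3 / (21.5 × √(2/23)) = 2.886. At m = 1 the critical value on 44 degrees of freedom is 2.015 and power is 80.6%; 23 is the smallest n that reaches 80%. A one-sided 5% test would need only 18 per arm. The stated 23 is therefore what an unadjusted two-sided 5% calculation gives.

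**Step 2: count the family from the text.** Three sub-analyses of the OAB-q give m = 3. One between-arm test for each of five outcomes gives m = 5. Five outcomes by three sub-analyses give m = 15.

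**Step 3: power of the primary between-arm test.**

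| m | α for the primary | Power, 23 per arm | Power, 25 per arm | n per arm for 80% |
|---|---|---|---|---|
| 1 | 0.05 | 80.6% | 83.9% | 23 |
| 3 | 0.0167 | 65.5% | 70.0% | 31 |
| 5 | 0.01 | 58.0% | 62.9% | 34 |
| 15 | 0.0033 | 42.5% | 47.6% | 42 |

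The 25-per-arm column assumes no attrition; with the attrition the plan expects, the 23-per-arm column is the relevant one. A simulation of 200,000 trials gave 80.6%, 65.3%, 57.9% and 42.5% at 23 per arm. A normal approximation is a little more generous (68.9% to 48.1% at 23 per arm for m = 3 to 15) but also well below 80%. Even m = 2 gives only 71.3% at 23 per arm and 75.5% at 25.

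**Step 4: how often the reading decides the verdict.** If the assumed benefit is real, the chance that p falls below 0.05 but not below 0.05/m at 23 per arm is the difference in power:

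- m = 3: 80.6 − 65.5 = 15.1%
- m = 5: 80.6 − 58.0 = 22.6%
- m = 15: 80.6 − 42.5 = 38.1%

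**Step 5: detectable difference.** At 23 per arm and 80% power, the detectable difference is 18.2 points at α = 0.05. It rises to 21.2, 22.5 or 25.2 points for m = 3, 5 or 15. Divided by 36.7, bilateral treatment would have to be 58%, 61% or 69% better than unilateral, against the 50% assumed.

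**The case against.** The best case for the plan is that its two sections need not conflict. A Bonferroni adjustment attached to pairwise tests is usually counted over pairs of groups within one outcome. With two arms there is one between-arm pair, so m = 1, the primary stays at 0.05 and the 80% stands. The single primary aim and single primary outcome fit that reading. It is also true that the plan never counts tests itself: three has direct textual support, while 5 and 15 come from multiplying out its lists. At m = 2 a p-value of 0.02 would still be positive. Finally, Bonferroni is conservative, so following the plan as written does not inflate the type I error.

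Part of this stands. Testing the primary at 0.05 may be what was intended, and the 42.5% end of the range belongs to the widest family only. But with m = 1 the written adjustment would adjust nothing on the between-arm side, and that reading passes over the three sub-analyses in the following sentence. No section states it. Nor does the conclusion depend on the larger families, since two tests are enough to take power below 80%. The conservatism of Bonferroni does not help either: the stated power is still not delivered, and the threshold is still open to choice.

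**Conclusion.** The concern holds. The alpha for the only primary test is undefined, and no Bonferroni family of two or more tests that includes it delivers the stated 80%. For 3 to 15 tests, power is 65.5% down to 42.5% at 23 per arm, and 70.0% down to 47.6% with all 25 analysed; only the 15-test reading falls below half. These figures rest on the plan's own difference and SD, a common SD, a two-sided test (assumed, and supported by the reproduction of 23 per arm), and the primary being inside the family, which is how the sentence reads. If the primary is in fact to be tested alone at 0.05, the stated power is right and the analysis section has to say so. Because the ambiguity can decide the trial's main conclusion, it must be settled before analysis.

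**What to change.** **Minimum change, one clause in Statistical Analysis.** State that the between-arm difference in OAB-q change from baseline to the last measurement is the single confirmatory test, at two-sided alpha 0.05, outside the Bonferroni family. This keeps the plan's own time point, agrees with its sample size section and restores the stated power, with no extra patients, visits or data. The clause should be fixed and dated before outcome data are examined, because on some readings it loosens the primary threshold; the document does not say whether data have been seen.

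**If the sponsor prefers to keep Bonferroni on the primary,** state the number of tests and restate the power at the adjusted alpha. The cost is either lower declared power or 31, 34 or 42 analysed per arm (62, 68 or 84 in total). Dividing by 0.90 for attrition and rounding up to equal arms gives 70, 76 or 94 recruited, against the planned 50.

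**Optional, about two sentences for the remaining tests.** Apply Bonferroni to the four secondary between-arm comparisons (0.05/4 = 0.0125 each), tested only if the primary is significant, and report within-arm changes as estimates with 95% confidence intervals. In simulation at 23 per arm, with assumed correlations between outcomes of 0, 0.5 or 0.8, this kept the overall error at 4.9% to 5.1% when no outcome differs and 1.8% to 3.9% when only the primary does. The price is that secondary claims become conditional on the primary and within-arm p-values are given up. The core problem can be resolved without this step.

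### Bonferroni is valid, but Holm's step-down procedure holds the same 5% familywise limit and never rejects less, so the plan may give up some power on the secondary outcomes

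*Combined protocol and SAP*

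**What the plan says.** All of this is in the combined protocol and SAP.

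- **Statistical Analysis, method:** "groups using a pairwise t-test (using a Bonferroni adjustment". No step-down or hierarchical procedure appears anywhere, so the natural reading is single-step Bonferroni.
- **Statistical Analysis, scope:** "For the analysis of primary and secondary outcomes, we will compare the last measurement to the baseline measurement within and between treatment groups". Five outcomes are listed: "OABq score, IIQ-7, daily number of voids, number of nighttime voids, and number of incontinence episodes". The section adds "These comparisons will result in three sub-analyses": within the unilateral arm, within the bilateral arm, and between arms. Neither the number of tests in the adjustment nor the divisor is given.
- **Study Design and Methods:** "Secondary outcomes will include change in the number of daily voids, change in nocturia or night time voids, change in number of incontinence episodes". With IIQ-7 as the quality-of-life measure, that makes four secondary outcomes.
- **Sample Size calculations:** only the primary outcome is sized, at "5% significance and 80 % power with a standard deviation of 21.5 will be: 23 per group for a total of 46 participants". No secondary outcome has an assumed effect, SD or power.

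**The concern.** Single-step Bonferroni holds every test in the family to the same strict threshold, however many of the others have already been rejected. Holm relaxes the threshold after each rejection and still keeps the familywise error at or below 5% under any dependence between the tests.

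The relaxation helps when several effects are real. That is plausible here: nighttime voids are part of the 24-hour count, leakage and IIQ-7 should be related, and Study Objectives describes success as improvement in the questionnaires together with fewer daily voids and nocturia episodes. In a trial of about 23 evaluable women per arm, power on the secondary outcomes is scarce. What is at stake is how many of them can be declared different between arms in support of an OAB-q benefit.

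**Working it through.** **Inputs from the documents (Sample Size calculations).** Mean decrease 36.7 (unilateral) and 55 (bilateral), SD 21.5, 5% significance, 80% power, 23 per group. With 25 recruited per arm and 10% attrition, 25 × 0.9 = 22.5, so 23 evaluable per arm is a fair working figure.

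**Assumptions.** Two-sided tests (sidedness is not stated); two-sample t-tests between arms; normal data; a family of the four between-arm secondary tests; common effect sizes of 0.30 to 0.85 SD; correlation 0.5, with 0 as a check.

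**Step 1. Reproduce the plan's figure.** d = (55 − 36.7)/21.5 = 18.3/21.5 = 0.85. The normal approximation gives n = 2(1.960 + 0.842)²/0.851² = 21.7, so 22. The t-test calculation gives 22.67, so 23 per group, with 80.6% power. The stated 23 reproduces with a two-sided, unadjusted 5%. A one-sided test would need only 17 to 18.

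**Step 2. The two rules for four tests.** Order the p-values from smallest to largest.

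- Bonferroni: reject each p ≤ 0.05/4 = 0.0125.
- Holm: compare in turn with 0.05/4 = 0.0125, 0.05/3 = 0.0167, 0.05/2 = 0.025 and 0.05/1 = 0.05, stopping at the first failure.

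The first Holm threshold is the Bonferroni threshold and the later ones are larger. Holm therefore rejects everything Bonferroni rejects, and it rejects something exactly when Bonferroni does.

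**Step 3. Power.** Simulated trials with 23 per arm and correlation 0.5, both rules applied to the same p-values, 20,000 to 40,000 trials per setting:

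| True effects | Power per real outcome, Bonferroni | Power per real outcome, Holm |
|---|---|---|
| All four 0.85 SD | 61% | 71% |
| All four 0.70 SD | 42% | 50% |
| All four 0.50 SD | 19.5% | 23.5% |
| All four 0.30 SD | 6.5% | 7.6% |
| Three at 0.85 SD, one null | 61% | 66% |
| One at 0.85 SD, three null | 61% | 61% |

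At 0.50 SD the expected number of rejections goes from 4 × 0.195 = 0.78 to 4 × 0.235 = 0.94. With correlation 0, Holm gives about 73% at 0.85 SD and 22% at 0.50 SD. The chance of at least one rejection is identical under the two rules in every setting (for example 88% at 0.85 SD and 44% at 0.50 SD, correlation 0.5).

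**Step 4. Familywise error.** With all four null, it is the same for both rules: about 4.9% at correlation 0 and 4.0% to 4.5% at correlation 0.5. With three real effects of 0.85 SD and one null, it is about 1.2% for Bonferroni and 3.2% for Holm, both under 5%.

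**Step 5. Dependence on the family.** The plan could be read as one family of 5 × 3 = 15 tests. Bonferroni then uses 0.05/15 = 0.0033 throughout. If all ten within-group tests were rejected first, Holm would test the smallest between-arm p-value at 0.05/5 = 0.01. The power of a t-test at those two levels is 42% and 58% at 0.85 SD, and 9% and 17% at 0.50 SD. The documents support early within-group rejection only for OAB-q (36.7/21.5 gives power above 99.9%).

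The primary test is affected too. At 23 per group its power is 80.6% at 5%, but 65.5% at 0.05/3, 58.0% at 0.05/5 and 42.5% at 0.05/15.

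**The case against.** The strongest reply is that nothing here is an error. Bonferroni is prespecified, valid under any dependence, and comes with simple matching simultaneous intervals. This stands: the point concerns efficiency.

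The reply continues that the gain is modest and cannot be shown for this trial. The 0.85 SD belongs to OAB-q alone. All four secondary effects being that large is doubtful, especially for incontinence episodes, since women without leakage may enrol and cannot improve on that count. At 0.50 SD or below, most real differences are missed under either rule because the trial is small. This also stands, and the size of the gain must be given as a range.

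Three stronger readings are tempting, and the documents do not support them:

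- *Real secondary differences will be missed because of Bonferroni.* They may be. Holm adds rejections only after one test has already passed Bonferroni.
- *Bonferroni buys nothing.* When some outcomes are null its actual familywise error is lower (about 1.2% against 3.2% in Step 4), and its simultaneous intervals are easier to form.
- *The secondary tests will be run at 0.0125.* The plan states no divisor, and its adjustment also covers the primary outcome and the within-group tests.

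A last objection is that Holm-adjusted p-values beside unadjusted 95% intervals can disagree. They can: at 0.50 SD, about 41% of simulated trials had an unadjusted interval excluding zero for an outcome that Holm did not reject. The same intervals beside Bonferroni disagree more often, in about 52%, so this calls for clear labelling and is not a reason to keep Bonferroni.

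**Conclusion.** The point holds as an improvement available at almost no cost. For whatever family is fixed, Holm has the same 5% limit as Bonferroni and at least its power. For a family of the four between-arm secondary tests, with 23 per arm and correlation 0.5, the gain per outcome is about 10 points if all four effects are 0.85 SD, about 4 points at 0.50 SD, about 1 point at 0.30 SD, and nil if only one effect is real. The chance of at least one secondary rejection is the same either way.

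Those figures rest on assumed effects, an assumed correlation and an assumed family, none of which the documents give. A reader should not infer that the plan's error control is faulty or that a particular loss has been shown. Because the sentence naming Bonferroni leaves its family undefined and takes in the primary and within-group tests, naming Holm alone would not be enough: the revision must also say how those other tests are treated.

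**What to change.** In Statistical Analysis, replace the Bonferroni clause with text to this effect:

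> The primary comparison is the between-arm difference in OAB-q change, tested once at a two-sided 5%. The four between-arm secondary comparisons (IIQ-7, voids per 24 hours, nighttime voids, incontinence episodes) form one separate family, tested by Holm's procedure at a two-sided familywise 5%. Holm-adjusted p-values will be reported; the accompanying 95% intervals are unadjusted and not for inference. Within-group changes are descriptive.

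Testing the primary outcome outside the family agrees with the unadjusted 5% used in Sample Size calculations.

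The cost is a few sentences, with no extra data and no change in conduct. There are two downsides. Simultaneous intervals are less simple to form than under Bonferroni, though the plan does not ask for any. And when some outcomes are truly null, the actual familywise error sits closer to 5%, while staying under it. The change should be made before outcomes are compared by arm.

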Study Protocol: Effectiveness of Bilateral PTNS compared to Unilateral PTNS for the Treatment of Overactive Bladder/Urge IncoNtinence (BUTTON)

Clinical trials: NCT 03535857

Protocol Date: 4/30/2024

Scientific Background

Overactive bladder (OAB) is defined as a syndrome of urinary urgency, usually associated with frequency with or without incontinence (1). This syndrome is estimated to affect more than 16 % of the adult population (2) and has a significant impact on the quality of life of those affected by it (3). The treatment algorithm as recommended by the American Urologic Association includes starting with behavioral modifications then offering pharmacologic therapy if needed (4). Previous data show that adherence to pharmacologic therapy is low due to side effects and thus there is a high discontinuation rate (5). One of the approved treatments with a low side effect profile is percutaneous posterior tibial nerve stimulation (PTNS) (4).

The SUmiT trial, a randomized controlled study for OAB has shown that when compared to sham, PTNS demonstrated 54% improvement in symptoms subjectively as compared to 20% in the sham arm. In addition, PTNS was associated with a better reduction of incontinence episodes and daily number of voids (6).

The OrBIT study which randomized women with OAB to PTNS or extended release tolterodine found a larger number of women receiving PTNS (79.5% vs. 60 %) who reported significant improvement in symptoms (7).

PTNS device has been cleared by FDA for the treatment of overactive bladder and urge urinary incontinence. It however does not state whether stimulation of the posterior tibial nerve should be performed unilaterally or bilaterally. The above studies using PTNS have all involved unilateral percutaneous stimulation of the posterior tibial nerve. We do not yet know whether bilateral stimulation produces a different result from the traditional unilateral stimulation.

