A study of sacral neuromodulation, also an approved second tier OAB treatment which stimulates the sacral nerve demonstrated that 76% of patients with bilateral lead implants had more than 50% improvement in overactive bladder symptoms as compared to 58% of those who had unilateral lead placement (8). A percutaneous nerve evaluation pilot study for those who failed sacral neuromodulation revealed that a select group of patients benefited from bilateral stimulation (9). There have been no bilateral PTNS studies for OAB to date. Though the colorectal literature suggests bilateral transcutaneous stimulation of the posterior tibial nerve improves fecal incontinence (10). The aim of our study is to compare the effectiveness of bilateral tibial nerve stimulation versus unilateral tibial nerve stimulation in managing overactive bladder symptoms using PTNS device. The study will not be evaluating the effectiveness of the device itself but rather comparing stimulation of one nerve versus two nerves using a device that is already on the market.

Study Objectives

Percutaneous tibial nerve stimulation (PTNS) is an accepted treatment for overactive bladder that can be accomplished in the office with minimal side effects. It is currently carried out by stimulating one of the posterior tibial nerve unilaterally.

The aim of this study is to determine whether bilateral percutaneous tibial nerve stimulation is more effective than unilateral stimulation.

Patients with a diagnosis of overactive bladder or urge incontinence who have previously failed lifestyle changes and/or pharmacologic therapy will be offered percutaneous tibial nerve stimulation. Enrolled patients will be randomized into two groups. The control group will receive the traditional unilateral treatment of PTNS. The intervention group will receive bilateral PTNS treatment during the study period. Intervention success will be measured by an improvement in the scores on the overactive bladder questionnaire and incontinence impact questionnaire as well as a decrease in the number of daily voids, nocturia episodes as assessed by voiding diaries.

Hypothesis

Bilateral PTNS is more effective than unilateral PTNS at reducing symptoms of OAB.

Primary Aim: Compare improvement of overactive bladder symptoms of participants receiving bilateral PTNS to those receiving unilateral PTNS using the overactive bladder questionnaire (OAB-q).

Secondary Aim(s):

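### Within-arm tests of change stand level with the randomised comparison, although with no sham arm they cannot isolate a PTNS effect and may use up its alpha

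*Combined protocol and SAP*

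**What the plan says.** In the combined protocol and SAP, the Statistical Analysis section covers the OAB-q, the IIQ-7, daily voids, nighttime voids and incontinence episodes. For these, "we will compare the last measurement to the baseline measurement within and between treatment groups", "using a pairwise t-test (using a Bonferroni adjustment"). It then lists three sub-analyses: "within the unilateral PTNS group, within the bilateral PTNS group, and between the groups". The section does not rank the three, call any of them descriptive, or say how many tests the adjustment covers.

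The rest of the document is comparative. The primary aim is: "Compare improvement of overactive bladder symptoms of participants receiving bilateral PTNS to those receiving unilateral PTNS". The Scientific Background closes with a disclaimer: "The study will not be evaluating the effectiveness of the device itself but rather comparing stimulation of one nerve versus two nerves". Study Design and Methods says of blinding that "we have elected not to use a sham needle", so both arms receive active stimulation.

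Study Objectives also contains this sentence: "Intervention success will be measured by an improvement in the scores on the overactive bladder questionnaire". It goes on to the other instruments and does not mention a difference between arms.

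**The concern.** The only randomised contrast in this trial is bilateral against unilateral. A test of change inside one arm has no comparator. It cannot tell stimulation from non-specific response, or from regression to the mean in women enrolled after earlier therapy failed. The protocol itself shows that improvement occurs without active treatment; of its cited sham-controlled trial it says that "PTNS demonstrated 54% improvement in symptoms subjectively as compared to 20% in the sham arm".

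Two things are at stake. First, interpretation: a within-arm p-value is likely to be small whether or not the second needle adds anything, yet the plan sets it beside the randomised test with no guidance on reading it. Second, alpha: if the within-arm tests count towards the Bonferroni adjustment, they take significance level from the one comparison that the trial was sized for.

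**Working it through.** **Inputs.** From Sample Size calculations: expected decrease 36.7 (unilateral) and 55 (bilateral), SD 21.5, 5% significance, 80% power, 23 per group. From Statistical Analysis: three sub-analyses, five outcomes, Bonferroni with the family size not given. Assumption: 21.5 is the SD of the change score. The documents give no change score for a sham arm, so a range is used.

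**Step 1: the plan's own figure.** Difference = 55 − 36.7 = 18.3. For a two-sample t-test at two-sided 5% and 80% power, noncentral t gives 22.67, so 23 per arm, as stated. Power at 23 per arm is 80.6%. The stated size therefore rests on one between-arm test at an unadjusted 5%.

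**Step 2: what a within-arm test detects.** Standard error of the mean change = 21.5/√23 = 4.48.
- At the planned unilateral change, t = 36.7/4.48 = 8.19. Power is essentially 100% in either arm.
- Smallest significant mean change = t(1 − α/2; 22 df) × 4.48. At 5%: 2.074 × 4.48 = 9.3 points. At 0.05/3: 2.591 × 4.48 = 11.6. At 0.05/15: 3.291 × 4.48 = 14.8.

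**Step 3: chance of within-arm significance if the whole change is non-specific** (noncentral t, n = 23).

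| Assumed mean change | α = 0.05 | α = 0.05/3 | α = 0.05/15 |
|---|---|---|---|
| 10 points | 57% | 38% | 18% |
| 15 points | 89% | 77% | 53% |
| 20 points | 99% | 96% | 86% |

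If bilateral stimulation adds nothing, the between-arm test at 5% rejects 5% of the time in every row.

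**Step 4: cost to the between-arm test** (difference 18.3, SD 21.5, 23 per arm; family sizes assumed).

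| Tests in the family | α per test | Between-arm power | Per arm for 80% |
|---|---|---|---|
| 1 (as sized) | 0.05 | 80.6% | 23 |
| 3 (three sub-analyses, one outcome) | 0.0167 | 65.5% | 31 |
| 5 (between-arm only, five outcomes) | 0.01 | 58.0% | 34 |
| 15 (three sub-analyses × five outcomes) | 0.0033 | 42.5% | 42 |

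The row for 5 tests shows that removing the within-arm tests does not by itself restore the planned power. OAB-q must also be tested alone at 5%.

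**The case against.** The strongest reply is that everything governing inference is comparative: the hypothesis, the primary aim, most of the secondary aims, the sample size and the third sub-analysis. The between-arm test is planned, and its estimate is the same whether or not within-arm tests are also run. Within-arm change is useful description. All of this stands, and it limits the point to interpretation and alpha.

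Three stronger readings are tempting, and the documents do not support them.

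- A reader might infer that the trial will report PTNS as effective. No section says so, and the Scientific Background says the device's effectiveness is not being evaluated. That the design could not answer that question follows from the lack of a sham arm; the protocol does not itself say so.
- A reader might take the success sentence in Study Objectives as a rule that lets bilateral PTNS be declared successful after a null comparison. The sentence lists instruments, follows a description of the two groups, and gives no threshold or test. It is loosely worded, not a decision rule.
- A reader might argue both that the two arms will almost certainly be significant and that the plan invites contrasting a significant arm with a non-significant one. For OAB-q these pull against each other. At the planning values a split result essentially never occurs. With equal true changes and independent arms at 5%, exactly one arm is significant with probability 2 × 0.569 × 0.431 = 49% at 10 points, but 2 × 0.892 × 0.108 = 19% at 15 and about 2% at 20. The split is a hazard only if changes are small. Nothing can be computed for the four secondary outcomes, for which the plan gives no planning values.

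The sham percentages quoted from the cited trial show that non-specific improvement happens. They do not give its size on the OAB-q scale, which is why a range is shown.

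**Conclusion.** The point holds in this limited form. The plan gives uncontrolled within-arm tests the same standing as its randomised comparison, and they do not address its hypothesis. A significant within-arm result would say little about PTNS, because changes of 10 to 20 points with no specific effect would reach 5% significance 57% to 99% of the time. If these tests share the Bonferroni family, power for the randomised comparison falls from 80.6% to 65.5% or 42.5%. This rests on 21.5 being the SD of change, on 23 analysed per arm, on assumed sizes of non-specific change, and on assumed families of 3 or 15 tests. The between-arm estimate is not biased by this. A change to the wording should be made, but the primary question is not undermined.

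**What to change.** - In Statistical Analysis, make the between-arm difference in change the only hypothesis test for each outcome, with OAB-q named as primary and tested at 5%. State which tests, if any, the Bonferroni adjustment still covers.
- Report within-arm changes as means with 95% confidence intervals, designated descriptive, outside the Bonferroni family, with a statement that they cannot be separated from non-specific change.
- In Study Objectives, reword the success sentence so that success means a between-arm difference in OAB-q change favouring bilateral PTNS.

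The cost is protocol and SAP wording: no new data, visits or participants. The small downside is the loss of within-arm p-values from the report.
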